6.5. Visit Windows

Data collected by daily diary will be summarized by the study treatment period (the initial 12 weeks, or the last 12 weeks). The last (initial) 12 weeks will be defined as below:

Treatment period	Collected days $\geq 84^*$	Collected days < 84
Initial 12 weeks	[date of Visit 3, date of Visit 3 + 84)	[date of Visit 3, date of Visit 6)
Last 12 weeks	[date of Visit 12, date of Visit 12 + 84)	[date of Visit 12, date of Visit 14]

* Collected days = (date of visit 6 – date of visit 3 + 1) for the initial 12 weeks ; Collected days = (date of visit 14 – date of visit 12 + 1) for the last 12 weeks.

Data analyzed by-visit-analysis (efficacy [excluding daily diary data], laboratory data, vital sign) will be summarized by the study scheduled visits described in the study protocol and SAP “Schedule of Events”. The analysis visit windows will be exhaustive so that all available values obtained from unscheduled visits and early termination (ET) visit have the potential to be summarized. No analysis visit windows will be applied for the study scheduled visits.

The analysis visit windows are created per study Schedule of Events (SOE) table for each parameter and will be applied if the data from study scheduled visits are unavailable. The following general rules will be applied to unscheduled visit and/or ET visit mapping for each parameter.

1. If ET due to an AE or lack of efficacy, the ET data for efficacy will not be mapped and the next scheduled visit data will be imputed using the worst score of all the observations in corresponding treatment group; if ET due to random reason, the ET data for efficacy will be mapped using rule 2 below. (Safety data will be mapped in either scenario.)
2. If ET visit falls in an analysis window which already has non-missing observed value of this parameter from the scheduled visit, ET will be mapped to the next scheduled visit.
3. If both ET visit and unscheduled visit of the same parameter are available in the same analysis visit window, only ET visit will be mapped.

4. If multiple unscheduled visits of the same parameter are available in the same analysis visit window, the unscheduled visits will be mapped using the following rules:
 - a. The closest unscheduled visit from the target day will be selected.
 - b. If multiple unscheduled visits exist on the same day, the first unscheduled visit will be used.
 - c. If the distance is a tie, the unscheduled visit after the target day of the scheduled visit will be used.
5. If mapping distance is greater than 6 weeks, the unscheduled visit will not be mapped.

Unscheduled visits and ET visit will be mapped per the following analysis visit windows based on the study day/visit of each parameter.

Analysis Visit Window for Efficacy Endpoints

Visit from SOE	Target Study Day*	PGIS, SPT for Cat and HDM	RQLQ, Spirometry, ACQ-5 for Asthma patients
Baseline	1	≤ 1	≤ 1
Visit 6	85	[2, 253]	[2, 211]
Visit 12	337		[212,379]
Visit 14 (EOT)	421	>253	>379

*Study days are calculated from the day of 1st injection. Study day = (date of assessment – 1st injection date + 1) when date of assessment \geq 1st injection date; otherwise, study day = (date of assessment – 1st injection date). If subject never received any dose of study drug, randomization date will be used in the place of 1st injection date.

Analysis Visit Window for Safety and Biomarkers

Visit from SOE	Target Study Day*	Vital Sign, Drug conc.	Hematology, Blood chemistry	ADA	Serum for sIgE for Fel d 2, 4, and 7	Biomarkers
Baseline	1	≤ 1	≤ 1	≤ 1	≤ 1	≤ 1
Visit 6	85	[2, 127]	[2, 127]	[2, 169]	[2, 253]	[2,211]
Visit 8	169	[128, 211]	[128, 211]			
Visit 10	253	[212, 295]	[212, 295]	[170, 295]		
Visit 12	337	[296, 379]	[296, 379]	[296, 379]		[212,379]
Visit 14 (EOT)	421	[380,463]	[380,463]	[380,463]	>253	[380,463]
Visit 15 (EOS)	505	> 463	> 463	> 463		> 463

* Study days are calculated from the day of 1st injection. Study day = (date of assessment – 1st injection date + 1) when date of assessment \geq 1st injection date; otherwise, study day = (date of assessment – 1st injection date). If subject never received any dose of study drug, randomization date will be used in the place of 1st injection date.

Post-baseline urinalysis will not be mapping since no scheduled measurements will be collected per protocol.

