Secondary endpoint – Continuous, FEV1, and ACQ-5	Percent change from baseline to week 12, week 60 FEV1 Change from baseline to week 60 in ACQ-5	FAS with asthma	
 4. Prohibited taken during the protocol defined window leading up to the relevant visit (week 12 or week 60) which are adjudicated to be handled using a hypothetical strategy^{3,4}: data will be set to missing and multiple imputation will be used. 5. Patient does not have exposure to cat leading up to assessment⁶: 
 a. If no cat is living in the patient's home leading up to assessment: all available data will be used in analysis (treatment policy) b. If patient is traveling away from home for less than 42 consecutive days prior to the assessment: all available data will be used in the analysis (treatment policy); otherwise (for travel \geq42 consecutive days), data will set to missing and multiple imputation will be used (hypothetical strategy) 	

Endpoint Category	Estimands			
	Endpoint(s)	Population	Intercurrent event(s) handling strategy and missing data handling	Population-level summary
			
In addition, if a patient has no available value of the relevant measurement at the specified visit, the imputation rules are as follows:
 
 • Missing data because of patients' discontinuation from study due to AEs and lack of efficacy will be imputed using worst score of all the observations in corresponding treatment group • Missing data due to any other reason will be imputed using MI. 	

[1] Note that for SPT endpoints, oral antihistamines are considered as prohibited medication, as specified in [Table 9](#)

[2] Category 1 of [Table 7](#) (RQLQ), [Table 8](#) (asthma), [Table 9](#) (SPT) lists prohibited medications that will be handled using a treatment policy

[3] Additional prohibited medications listed in Category 2 of [Table 7](#), [Table 8](#), and [Table 9](#) will undergo blinded adjudication by study medical monitor before the database lock to determine they will be handled by treatment policy, composite strategy, or hypothetical strategy

[4] Prohibited medications that are not indicative of treatment failure and will be handled by hypothetical strategy are defined in Category 3 of [Table 8](#) and [Table 9](#)

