5.6.3. Adjustment for Multiple Comparisons

A non-binding futility interim analysis (IA) is planned in this study (details are provided in Section 7) and an administrative penalty of 0.001 will be taken from the significance level used at final analysis, and thus 2-sided 0.049 will be used. No further multiplicity adjustment will be performed for the IA.

The following multiplicity adjustment approach, a hierarchical procedure, will be used to control the overall Type-1 error rate at 0.049 for the primary endpoint and the secondary endpoints of R1908-1909 versus placebo. Each hypothesis will be formally tested only if the preceding one is significant at the 2-sided 0.049 significance level. The hierarchical testing order is shown in below table (all comparisons are with the placebo).

Level	Endpoints	Testing Order
Primary endpoint	Daily CSMS, averaged over the last 12 weeks of the treatment period (weeks 48 to 60)	1
Secondary endpoints	Daily TNSS, averaged over the last 12 weeks of treatment period (weeks 48 to 60)	2
	Percent change from baseline to the end of treatment (week 60) in cat SPT mean wheal diameter	3
	Percent change from pre-treatment baseline in average TNSS, over the last 12 weeks of the treatment period (weeks 48 to 60)	4
	Daily CSMS, averaged over the initial 12 weeks of the treatment period (weeks 0 to 12)	5
	Daily TNSS, averaged over the initial 12 weeks of treatment period (weeks 0 to 12)	6
	Daily TSS, averaged over the last 12 weeks of the treatment period (weeks 48 to 60)	7
	Daily TSS, averaged over the initial 12 weeks of the treatment period (weeks 0 to 12)	8
	Percent change from pre-treatment baseline in average CSMS, over the last 12 weeks of the treatment period (weeks 48 to 60)	9
	Change from baseline to week 60 in RQLQ(S)+12	10
	DMS, averaged over the last 12 weeks of the treatment period (weeks 48 to 60)	11
	Daily TOSS, averaged over the last 12 weeks of the treatment period (weeks 48 to 60)	12
	Percent change from pre-treatment baseline in average TSS, over the last 12 weeks of the treatment period (weeks 48 to 60)	13

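### The 6-week mapping limit in SAP 6.5 omits early-termination visits, so a skin prick test taken months early can stand as the week-60 value; the order of mapping and multiple imputation is not stated

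*SAP*

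**What the plan says.** **Mapping rules (SAP 6.5, Visit Windows).** The analysis windows "will be applied if the data from study scheduled visits are unavailable". The rules work parameter by parameter: "The following general rules will be applied to unscheduled visit and/or ET visit mapping for each parameter". Under rule 1, an ET for an adverse event or lack of efficacy is not mapped for efficacy and takes the worst score of the treatment group. For other withdrawals, "if ET due to random reason, the ET data for efficacy will be mapped using rule 2 below". Rule 2 covers an ET visit in a window that already has a scheduled value: "from the scheduled visit, ET will be mapped to the next scheduled visit". Rule 5 reads: "If mapping distance is greater than 6 weeks, the unscheduled visit will not be mapped". Rules 3 to 5 use ET visit and unscheduled visit as separate terms.

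**Windows.** The efficacy table gives SPT a Visit 6 window of days 2 to 253. Its week-60 row is "Visit 14 (EOT) 421 >253 >379", where the first limit is for SPT and PGIS and the second for RQLQ, spirometry and ACQ-5.

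**Imputation (SAP 5.6.2, Table 5).** The imputation rules apply when a patient has no available value at the specified visit. Discontinuation for adverse events or lack of efficacy gets the worst score. Otherwise, "Missing data due to any other reason will be imputed using MI".

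**Testing order (SAP 5.6.3).** Third in the fixed sequence is "Percent change from baseline to the end of treatment (week 60) in cat SPT mean wheal diameter". RQLQ(S) at week 60 is tenth.

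**The concern.** The SAP treats 6 weeks as the furthest an off-schedule value may be moved, yet as written that tolerance does not bind the visit type most likely to be far from its target. The schedule of events includes the cat SPT in the end-of-treatment/early-termination column, so withdrawing patients who attend will usually have such a value.

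If mapping is run before imputation, these patients contribute a single value carried forward to week 60 and treated as observed, with none of the between-imputation variance that MI would add. The value also belongs to a different exposure state. A patient last dosed on day 253 or earlier would be at least 421 − 253 = 168 days off drug at week 60. With the half-lives in Protocol 3.2.2 (31.0 and 22.4 days), that is at least 168/31.0 = 5.4 and 168/22.4 = 7.5 half-lives.

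The week-60 SPT test gates orders 4 to 13, which is ten hypotheses. If the order of mapping and MI stays open, two programmers could build different week-60 datasets for that test.

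**Working it through.** **Inputs.** Target days are 85 (Visit 6), 337 (Visit 12) and 421 (Visit 14), from the SAP 6.5 window table. The limit is 6 weeks = 42 days (rule 5). Planned dropout is 20% by week 60 with 315 per arm (SAP 2.3).

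**Step 1: reproduce the window boundaries.** Each is the midpoint of adjacent target days.
- SPT, Visit 6/Visit 14: (85 + 421)/2 = 253, as stated.
- RQLQ, Visit 6/Visit 12: (85 + 337)/2 = 211, as stated.
- RQLQ, Visit 12/Visit 14: (337 + 421)/2 = 379, as stated.

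**Step 2: follow an ET SPT through the rules** (withdrawal for another reason, nominal schedule). Distance = 421 − ET day.

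| ET day | Route to week 60 | Days early | Weeks early |
|---|---|---|---|
| 86, Visit 6 SPT done on day 85 | rule 2 | 335 | 47.9 |
| 253, Visit 6 SPT done | rule 2 | 168 | 24.0 |
| 254 | directly in the window | 167 | 23.9 |
| 378 | directly in the window | 43 | 6.1 |
| 379 | directly in the window | 42 | 6.0 |

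If Visit 6 took place at the early edge of its ±14-day window (day 71), an ET on day 72 would be 421 − 72 = 349 days early. If the Visit 6 SPT was never done, an ET up to day 253 fills Visit 6 instead and week 60 is untouched.

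**Step 3: RQLQ(S).** An ET on day 338, after Visit 12 on day 337, lies in the window for days 212 to 379. That window is filled, so rule 2 moves the value to Visit 14: 421 − 338 = 83 days early. Spirometry and ACQ-5 share this window column.

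**Step 4: apply the 42-day limit to ET visits.** The earliest ET day that can count as week 60 becomes 421 − 42 = 379, and the maximum distance falls from 335 to 42 days.

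**Step 5: how often the limit would bite.** The documents give no ET timing. As an illustration only, if ET days were uniform over days 86 to 420, (379 − 86)/(421 − 86) = 293/335, or about 87% of mapped SPT values, would be more than 6 weeks early.

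**Step 6: number of patients.** The only anchor is 0.20 × 315 = 63 withdrawals per arm for all reasons (the SAP rounds to about 64). The split by reason, timing and ET attendance is not given, so the affected number cannot be derived.

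**Step 7: order of the rules.** Mapping in 6.5 and MI in Table 5 are both triggered by a missing scheduled week-60 value. SAP 6.4 says the missing-data rules for efficacy are in 5.6.1 and 5.6.2. No section says which step runs first.

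**The case against.** **Contradiction.** A reader might infer that 6.5 flatly contradicts the MI in Table 5. The documents do not support that. Table 5 is conditional on having no available value, and 6.5 can be read as defining which value is available. Map first, then impute what remains, is coherent. Protocol Table 6 leans the other way: for SPT it ties imputation to having no value during the 12-week assessment period, and an ET before day 337 lies outside weeks 48 to 60. But the SAP rewords that condition to the specified visit. What stands is an unstated order plus a missing limit.

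**Bias.** A reader might also infer that the SPT effect is overstated by a calculable amount. It is not calculable. The documents give no wheal suppression at ET or off drug. MI under missing-at-random would draw mainly on patients still observed at week 60, so it would not recover an off-drug value either. The supportable harms are a mistimed value and missing imputation variance.

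**Reach.** Several filters shrink the group. Withdrawals for adverse events or lack of efficacy are excluded by rule 1. Patients who stop drug are encouraged to stay for all visits (Protocol 8.3.2). Oral antihistamine within 5 days of an SPT is Category 3 (SAP Table 9), so some ET tests could be set to missing and go to MI. ET on day 86 is a limiting case. All of this is fair. It limits the count but does not close the gap for ET on later days.

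**Reading of rule 2.** The next scheduled visit could mean any clinic visit. The per-parameter wording and the SPT window table point to Visit 14.

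**Importance.** Daily diary endpoints, including the primary, are outside this mapping, and nothing shows that the third-ranked test would change.

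**Conclusion.** The point holds on the text. Rule 5 limits unscheduled visits only. An ET cat SPT from a patient who leaves for a reason other than an adverse event or lack of efficacy can therefore be analysed as observed week-60 data with no distance limit: up to 335 days early through rule 2, or 167 days early by direct entry to the window. RQLQ(S) can be up to 83 days early. These figures assume visits on their target days, attendance at the ET visit, a usable ET measurement, and a completed Visit 6 (SPT) or Visit 12 (RQLQ) value where rule 2 is the route.

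Whether such values displace MI depends on an order the SAP leaves open. If mapping comes first, the third-ranked test carries mistimed values without imputation uncertainty. Neither the number of patients nor the size or direction of any bias in the treatment difference can be established from the documents. The change is worth making before database lock; the primary analysis is not affected.

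**What to change.** 1. In rule 5, name ET visits alongside unscheduled visits, so that neither is mapped beyond 6 weeks.
2. For efficacy data, say that this limit governs both rule 2 and ET values that fall directly in a window. For SPT, only ET tests on day 379 or later could then count as week 60.
3. State the order in 6.5 and Table 5: mapping is applied first, and MI under Table 5 then handles patients still without a value. The worst-score rule for adverse events and lack of efficacy is unchanged.

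It may be tempting to add the ET value as a predictor in the imputation model. That should not be done: withdrawn patients attend ET assessments only (Protocol 9.1.2), so no patient has both an ET and a later scheduled week-60 SPT, and the association cannot be estimated without further assumptions.

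The cost is a few words in rule 5, a sentence on order and a small programming change. The downside is that slightly more patients are imputed. SAP Section 1 allows revision on blinded review before data lock.

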6.6. Statistical Technical Issues

None.

7. INTERIM ANALYSIS

7.1. Futility Interim Analysis

A non-binding futility interim analysis (IA) in the study is planned to be performed when at least 40% of randomized patients have completed the week 12 visit or discontinued before week 12. There is no plan to change the conduct of this trial except a possibility to stop the trial due to unfavorable benefit-risk. The IA will be performed by independent statisticians that support the IDMC and who are separate from personnel involved in the trial conduct. The IDMC will review the unblinded IA results and recommend action based on the non-binding futility criteria based on CSMS and TNSS that will be specified in Section 7.2.

If the non-binding futility criteria are met, the unblinded results will be viewed by a small group of senior sponsor individuals, who are separate from sponsor personnel involved in the conduct of the study. Individuals involved in the conduct of the study (i.e., patients, Investigators, Study Team, and Project Team, etc.) will have no access to the IA results.

The analysis population for the interim futility analysis will include at least the first 40% of the randomized patients. An administrative penalty of 0.001 will be taken from the significance level used at final analysis (i.e., 2-sided 0.049 will be used for the final analysis).

7.2. Interim Futility Criteria

Futility will be assessed using criteria based on the following two efficacy endpoints:

- Daily CSMS, averaged over the initial 12 weeks of the treatment period (weeks 0 to 12), in patients who receive REGN1908-1909 versus placebo
- Daily TNSS, averaged over the initial 12 weeks of treatment period (weeks 0 to 12), in patients who receive REGN1908-1909 versus placebo

For the IA, the efficacy will be analyzed using the same methods described in the efficacy analyses section (Section 5.6). The least squares means estimates for these two endpoints for each treatment group, as well as the difference between the REGN1908-1909 and placebo will be provided based on an ANCOVA model, with the treatment group, randomization stratification factors (as stratified), and cat sIgE (<17.5 kUa/L versus ≥ 17.5 kUa/L) as fixed effects and the baseline CSMS/TNSS as a covariate. This ANCOVA model as the primary analysis in the study will be conducted for the IA.

Based on these estimates, the standardized effect size and percent reduction in average CSMS and average TNSS for REGN1908-1909 relative to placebo will be calculated. The two steps below will be followed to assess futility:

Step 1: Assess CSMS endpoint. Futility criteria for CSMS will be met if:

- a. Mean difference between REGN1908-1909 and placebo is $< 5\%$
or
- b. Effect size (mean diff./SD) $< 0.073^*$

(* Note: The effect size of 0.073 corresponds to an assumed mean difference in CSMS of 0.455 and a standard deviation of 6.2.)

If neither a. nor b. is met for CSMS, then futility criterion is not met and the study will proceed as planned. If either criteria a. or b. are met, the TNSS endpoint will be evaluated in step 2.

Step 2: Assess TNSS endpoint. Futility criteria for TNSS will be met if:

- a. Mean difference between REGN1908-1909 and placebo is <5%
- or**
- b. Effect size (mean diff./SD) < 0.072**

(** Note: The effect size of 0.072 corresponds to an assumed mean difference in TNSS of 0.165 and a standard deviation of 2.3.)

If neither a. nor b. is met for TNSS, then the study will proceed as planned. If either criteria a. or b. are met, the non-binding futility criteria have been met and unblinded results will be reviewed by a small group of senior sponsor individuals.

7.3. Timing of Unblinded Primary Analysis

The unblinded primary analysis may be performed when the last patient completes 60 weeks of treatment duration (or discontinues prior to week 60) in order to expedite the submission to regulatory agencies. No changes in the conduct of the study will be made based on this primary analysis. The assessment of primary and secondary endpoints performed during the analysis will be the final analysis of the primary endpoint and secondary endpoints and 2-sided alpha of 0.049 will be used.

8. SOFTWARE

All analyses will be done using SAS Version 9.4 or above or using R Version 3.5 or above.

10. APPENDIX

10.1. Summary of Statistical Analyses

10.1.1. Summary of Efficacy Analyses

Endpoint	Analysis Populations	Primary Analysis	Supportive Analysis	Subgroup Analysis	Other Analyses
Primary Endpoint					
Daily CSMS, averaged over the last 12 weeks of the treatment period (weeks 48 to 60)	FAS	ANCOVA model with treatment group, stratification factors, and cat sIgE (<17.5 kUa/L versus ≥ 17.5 kUa/L) as fixed factors and baseline CSMS as a covariate	Yes - All intercurrent events handled via a treatment policy	Yes	Plot
Secondary Endpoints					
Daily TNSS, TSS, CSMS, TOSS, and DMS over the last 12 and the initial 12 weeks of the efficacy assessment period (weeks 48 to 60, and weeks 0 to 12) and the percent change from baseline in these endpoints (except for daily CSMS over the last 12 weeks)	FAS	ANCOVA model with treatment group, stratification factors, and cat sIgE (<17.5 kUa/L versus ≥ 17.5 kUa/L) as fixed factors and relevant baseline measurement as a covariate	N/A	Yes	Plot
Percent change from baseline to week 12 cat SPT mean wheal diameter Percent change from baseline to end of treatment (week 60) cat SPT mean wheal diameter Change from baseline to week 60 in RQLQ(S)+12	FAS	ANCOVA model with treatment group, stratification factors, and cat sIgE (<17.5 kUa/L versus ≥ 17.5 kUa/L) as fixed factors and baseline SPT mean wheal diameter as a covariate	N/A	Yes	Plot
Percent change from baseline to week 12 FEV1 Percent change from baseline to week 60 FEV1 Asthma daily symptom score (ADSS), averaged over the last 12 weeks and the initial 12 weeks of the treatment period (weeks 48-60, weeks 0 to 12) Change from baseline to week 60 in ACQ-5	FAS with asthma	ANCOVA model with treatment group, stratification factors, and cat sIgE (<17.5 kUa/L versus ≥ 17.5 kUa/L) as fixed factors and relevant baseline measurement as a covariate	N/A	Yes	Plot

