# Baseline Period within Screening:

The baseline assessment period is up to 21 days, and should be completed for a minimum of 15 consecutive days during the approximately 12-week screening period. This period is utilized to demonstrate that patients are sufficiently symptomatic due to cat exposure while taking standard of care anti-allergy rescue medications provided during the study (oral antihistamine, antihistamine eye drops, intranasal corticosteroid; Section 8.2). Patients will complete an e-diary to record their nasal, ocular, and asthma symptoms as well as anti-allergy rescue medication use up to a 3-week period during screening (the 3-week period allows for up to 6 days of training or troubleshooting, if required). Patients will be required to have experienced allergic rhinoconjunctivitis symptoms, as measured by the TSS, and to have used anti-allergy rescue medications, as specified, for at least 8 days of a consecutive 15-day period during this time. Patients must meet a daily total rhinitis and conjunctivitis symptom threshold of at least 8 of 18 on at least 8 days of the consecutive 15-day baseline assessment period and use standard therapeutic doses of the anti-allergy rescue medications on 8 of the consecutive 15 days during the baseline assessment period. Adequate standard of care treatment is defined as currently approved doses of antihistamines and intranasal corticosteroids provided during the study.

The baseline assessment will occur outside of relevant pollen season for those patients with seasonal allergies.

Patients will complete baseline Patient Global Impression of Severity (PGIS) and RQLQ(S) during the baseline assessment period. Additionally, patients with asthma will complete the Asthma daytime and nighttime symptom diaries (ADSD and ANSD), ACQ-5, nighttime awakenings, and asthma rescue medication use during the baseline assessment period.

If missing data are reported due to documented e-diary malfunction (eg, technical issues that are reported to the vendor), then the baseline assessment period may be extended accordingly, allowing the 15-day period to be re-started, to ensure that a consecutive 15 day period can be obtained. In such a circumstance, the medical monitor should be consulted, and agreement must be obtained with the sponsor.

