# 11.4.10. Analysis of Quality of Life Data

Quality of life data will be analyzed using the same method as specified for the continuous secondary efficacy variables.

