5.6.2. Analysis of Secondary Efficacy Variables

The secondary efficacy endpoints will be analyzed using an ANCOVA model in the same fashion as the primary analysis of the primary endpoint.

Average Daily Symptom Score Endpoints (TOSS, TNSS, DMS, TSS)

The average TOSS, TNSS, and DMS will be calculated using all observed daily scores during the specified time period (initial 12 weeks or last 12 weeks of the treatment period).

The average TSS will be calculated by adding average TNSS and average TOSS during the specified time period (initial 12 weeks or the last 12 weeks of the study).

The intercurrent events, strategies, and the corresponding missing data handling approaches for these endpoints will follow the same strategy as for the primary endpoint, outlined in [Table 4](#).

Supplemental analyses using non-parametric methods, such as Wilcoxon ranked sum test or Hodges-Lehmann analysis of median differences, may be performed in the event of a violation of the normality assumption.

Asthma-related endpoints (ADSS, FEV1, ACQ-5)

All asthma endpoints will be analyzed on patients in the FAS with asthma (all randomized patients with ongoing asthma in medical history). Supplemental analyses may be performed in the subset of ongoing asthma patients who were also on asthma medication at baseline.

All available daily ADSS will be averaged over the specified time period (initial 12 weeks or last 12 weeks of the treatment period). If ADSD or ANSD is missing on any given day, ADSS score for that day will be considered missing and no value will be calculated. In addition, ANSD will be shifted by one day, i.e., ADSD on Day 1 and ANSD on Day 2 will be used to get the ADSS on Day 1, ADSD on Day 2 and ANSD on Day 3 will be used to get the ADSS on Day 2, and so on. The day before Visit 6 or Visit 14 for the initial 12 weeks and last 12 weeks, respectively, will be the last day that contributes to the average ADSS (since there will generally be no ANSD measurement corresponding to the date of Visit 6 or 14).

The estimand for ADSS will follow the same approach as for the primary endpoint, described in [Table 4](#). Separate analyses of average ADSD and average ANSD may also be performed.

Estimands for FEV1 and ACQ-5 are specified in [Table 5](#). A supplemental analysis may be performed for the change from baseline ACQ-5 endpoint only in patients with baseline ACQ-5 > 1.5.

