Supplemental analyses using non-parametric methods, such as Wilcoxon ranked sum test or Hodges-Lehmann analysis of median differences, may be performed in the event of a violation of the normality assumption.

Prohibited medications and corresponding data utilization methods relevant for asthma endpoints are specified in [Table 8](#)

SPT endpoints

The intercurrent events, strategies, and the corresponding missing data handling approaches for the SPT endpoints are outlined in [Table 5](#).

Prohibited medications and corresponding data utilization methods relevant for SPT endpoints are specified in [Table 9](#)

Table 5: Summary of Estimands for Secondary Endpoints of Clinical Importance

Endpoint Category	Estimands			
	Endpoint(s)	Population	Intercurrent event(s) handling strategy and missing data handling	Population-level summary
Secondary endpoint – Continuous, SPT, and RQLQ(S)+12	Percent change from baseline to week 12 and end of treatment (week 60) cat SPT mean wheal diameter Change from baseline to week 60 in RQLQ(S)+12	FAS	
The intercurrent events will be handled as follows⁵:
 
 1. Discontinuing the study intervention: all data collected after discontinuation will be used in the analysis (treatment policy strategy) 2. Rescue treatment¹ and select prohibited medications^{2,4} to treat allergic symptoms during the efficacy assessment period: data after allergy-relieving rescue medication will be used in the analysis (treatment policy strategy) 3. Prohibited medications taken during the protocol defined window leading up to the relevant visit (week 12 or week 60) which are adjudicated to be handled using a composite strategy⁴: data will be set to missing and imputed using the worst value of all observations in corresponding treatment group. 	
ANCOVA model with treatment group, stratification factors, and cat sIgE (<17.5 kUa/L versus \geq17.5 kUa/L) as fixed factors and relevant baseline measurement as a covariate.
 
LS-means estimates will be provided for each treatment group, as well as the difference between REGN1908-1909 and placebo with corresponding 95% confidence interval and 2-sided p-value.

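### SAP 10.1.1 gives week-60 change in RQLQ(S)+12, step 10 of the testing hierarchy, the skin-prick wheal as its baseline covariate, where SAP Table 5 calls for the endpoint's own baseline

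*SAP*

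**What the plan says.** SAP 10.1.1 has one row for three endpoints: percent change in cat wheal at week 12, the same at week 60, and week-60 change in RQLQ(S)+12. The row states one model, an ANCOVA with treatment, stratification factors and cat sIgE "as fixed factors and baseline SPT mean wheal diameter as a covariate". It names no other continuous covariate.

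SAP Table 5, in section 5.6.2, has the matching row, labelled "Continuous, SPT, and RQLQ(S)+12". Its model takes the same factors "as fixed factors and relevant baseline measurement as a covariate". The text of 5.6.2 sets the general rule: "The secondary efficacy endpoints will be analyzed using an ANCOVA model in the same fashion as the primary analysis of the primary endpoint". The primary model in 5.6.1 adjusts for baseline CSMS, that is, for its own baseline. Protocol 11.4.10 adds: "Quality of life data will be analyzed using the same method as specified for the continuous secondary efficacy variables".

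SAP 5.6.3 lists "Change from baseline to week 60 in RQLQ(S)+12" as order 10 of 13, under the rule "Each hypothesis will be formally tested only if the preceding one is significant at the 2-sided 0.049 significance level".

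**The concern.** The SAP states two covariates for one confirmatory test. A programmer working from the summary table would adjust RQLQ(S) for a skin-test measurement and leave out baseline RQLQ(S).

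A change score that is not adjusted for its own baseline usually has a larger residual variance, so the test usually has less power. Because testing is sequential, a failure at step 10 also stops formal testing of DMS, TOSS and percent change in TSS over weeks 48 to 60 (steps 11 to 13).

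**Working it through.** **1. Which covariate do the documents support for RQLQ(S)?**

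| Place | Endpoints covered | Continuous covariate |
|---|---|---|
| SAP 10.1.1, skin-prick row | two wheal endpoints and RQLQ(S)+12 | baseline wheal |
| SAP Table 5 | the same three | the relevant baseline |
| SAP 5.6.2, general rule | all secondary efficacy endpoints | as for the primary: own baseline |
| Protocol 11.4.10 | quality of life | as for continuous secondary endpoints |
| Protocol Table 6, skin-prick row | wheal endpoints only | baseline wheal |
| SAP 10.1.1, daily-score and asthma rows | those endpoints | the relevant baseline |

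Only the first row gives RQLQ(S) the wheal. The likely cause, though this is inference, is that RQLQ(S) was added to a row carried over from Protocol Table 6 and the covariate was not changed.

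Baseline RQLQ(S) is available. Protocol 6.1 says "Patients will complete baseline Patient Global Impression of Severity (PGIS) and RQLQ(S) during the baseline assessment period", the Schedule of Events has it at the randomization visit, and SAP 4.1 lists it as a baseline characteristic.

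**2. The plan's own figure.** The documents give no SD, effect or power for RQLQ(S). The only design figure to check is the one for CSMS in SAP 2.3 (difference 1.8, SD 6.2, two-sided alpha 0.049, 90% power):

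n per arm = 2 × (z₀.₉₇₅₅ + z₀.₉₀)² × (6.2/1.8)² = 2 × 3.250² × 11.86 = 250.6, so 251 as stated.

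With 20% dropout, 251/0.8 = 313.75, or 314 against the stated 315. Both agree well enough. The 251 per arm is used below only as an illustration.

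**3. Precision with equal SDs.** Let r be the correlation between baseline and week-60 RQLQ(S), and suppose that wheal is unrelated to RQLQ change. In units of the common variance, the residual variance of the change is 2(1 − r) without baseline RQLQ(S) and 1 − r² with it. The ratio is 2(1 − r)/(1 − r²) = 2/(1 + r). The power column takes a test that has 90% power under the Table 5 model: Φ(3.250/√ratio − 1.969).

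| r (assumed) | Variance ratio | SE larger by | 90% power becomes | 251 per arm is worth |
|---|---|---|---|---|
| 0.3 | 1.54 | 24% | 74% | 163 |
| 0.4 | 1.43 | 20% | 77% | 176 |
| 0.5 | 1.33 | 15% | 80% | 188 |
| 0.6 | 1.25 | 12% | 83% | 201 |
| 0.7 | 1.18 | 8% | 85% | 213 |

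**4. Relaxing the assumptions.** If the week-60 SD is k times the baseline SD, the ratio is (1 + k² − 2rk)/[k²(1 − r²)].

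| k | r = 0.3 | r = 0.5 | r = 0.7 |
|---|---|---|---|
| 0.8 | 1.99 | 1.75 | 1.59 |
| 1.0 | 1.54 | 1.33 | 1.18 |
| 1.2 | 1.31 | 1.15 | 1.03 |
| 1.5 | 1.15 | 1.04 | 1.00 |

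The same ratio can be written 1 + (1 − rk)²/[k²(1 − r²)]. With an uninformative wheal it is therefore never below 1, and it equals 1 when rk = 1.

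If wheal correlates 0.3 with RQLQ change, every ratio is multiplied by 1 − 0.3² = 0.91. At k = 1 this gives 1.40, 1.21 and 1.07 for r = 0.3, 0.5 and 0.7. In the corner k = 1.5, r = 0.7 it gives 1.002 × 0.91 = 0.91. A loss is usual but not certain.

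**5. Validity.** In a simulation of 2,000 trials with complete data (r = 0.5, equal SDs, 251 per arm, true difference −0.251), the mean estimate was −0.249 with the wheal and −0.251 with baseline RQLQ(S). Type I error was 4.8% and 4.3% against a nominal 4.9%. Power was 79.5% and 90.0%, and the variance ratio was 1.34.

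**The case against.** The strongest reply is that SAP 5.6.1 places the description of the efficacy analyses in its own subsections and presents 10.1.1 as their summary. On that reading section 5.6 is the specification. It is internally consistent and the protocol agrees with it, so one appendix cell is out of step and a careful statistician would follow Table 5. This largely stands, and it is why the point is minor. It does not make the cell right: the SAP states no rule on which text prevails, and summary tables are what programmers tend to work from.

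Three stronger readings are tempting, and the documents do not support them.

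- A reader might infer that the covariate is an open choice to be settled after unblinding. SAP section 1 requires revisions to rest on blinded review, with a final plan before data lock and code breaking. Choosing the wheal would contradict Table 5 and 5.6.2, and it would usually be the less powerful model.
- A reader might infer a biased comparison through chance imbalance in baseline RQLQ(S). Under randomization either model is unbiased with type I error controlled. Chance imbalance is the precision loss described another way, not a second harm.
- A reader might take a 25% to 43% larger variance as the known cost. That range rests on an assumed r, equal SDs and an uninformative wheal. No passage establishes how prognostic baseline RQLQ(S) is.

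The hierarchy consequence is also remote. It needs nine earlier successes, use of the wrong cell, and a result near the threshold. SAP 4.5.3 classes week-60 RQLQ(S) among the other secondary endpoints. Of the six key secondary endpoints, only percent change in TSS (step 13) lies after it.

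**Conclusion.** The summary row is wrong as written for week-60 change in RQLQ(S)+12 and contradicts SAP Table 5 and 5.6.2. It is an inconsistency between appendix and body; the analysis chosen in 5.6 is sound.

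If the row were followed, the harm would be lost precision in most plausible cases. Under the equal-SD assumptions the variance would be 1.43 to 1.25 times as large for r of 0.4 to 0.6. With wheal still unrelated to RQLQ change, the range is about 1.0 to 2.0 over r of 0.3 to 0.7 and a week-60 SD of 0.8 to 1.5 times baseline. All these inputs are assumptions, so the figures are illustrative. The primary endpoint and hierarchy steps 2 to 9 are untouched.

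**What to change.** In the skin-prick row of SAP 10.1.1, replace the covariate clause with the one in Table 5, "as fixed factors and relevant baseline measurement as a covariate". It serves the wheal endpoints and RQLQ(S) alike. The alternative is to give RQLQ(S)+12 its own row with baseline RQLQ(S) as covariate. Make the change before database lock.

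The cost is one table row in the SAP. No new data, sample-size change or change in trial conduct is needed.
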